## ABSTRACT

### Context:

African and African American individuals are inadequately represented in clinical trials data—impacting the relevance of these trials to diseases that affect them. Although studies have demonstrated the value of video, little is known about the value of incorporating appeals to promote inclusion.

### Objectives:

This study will assess whether video-based inclusion appeals improve African American children's enrollment into the Children's Hospital of Philadelphia (CHOP) research study registry.

### Study Design:

The study will consist of two phases: a qualitative research phase and a randomized controlled trial phase.

### Setting/Participants:

Phase 1 involves parents from the CHOP Research Family Partners and utilizes consensus/voting to review study design and materials. Phase 2 takes place in the CHOP primary care waiting rooms. Ninety parents who self-identify as English-speaking African/African American adults will be enrolled.

### Study Interventions and Measures:

Phase 1 has been described above. Phase 2 study participants will complete a demographic survey, before being randomized to receive one of three interventions:

1. Short description of the registry
2. video with inclusion appeal, questions about the perceived effectiveness of the video
3. video without inclusion appeal, questions about the perceived effectiveness of the video.

[figure not shown]
All participants will be invited to join a study enrollment registry.

## SCHEDULE OF STUDY PROCEDURES

Study Phase 1	Group Meeting	Group Meeting	Group Meeting	Group Meeting
Visit Number	1	2	3	4
Informed Consent/Accent	X			
Project discussion	X	X	X	X
Video review		X	X	
Video discussion		X	X	
Video evaluation		X	X	
Enrollment plan	X			X

Study Phase 2	Screening	Intervention
Visit Number	1	1
Study Days	1	
Informed Consent/Accent	X	
Review Inclusion/Exclusion Criteria	X	
Randomization	X	
Demographics/Medical History		X
Survey (video embedded if being shown)		X
Registry enrollment question		X

## STUDY DIAGRAM

## 1 BACKGROUND INFORMATION AND RATIONALE

### 1.1 Introduction

Improving diversity in research projects and national data repositories is critical to providing safe and effective care to marginalized groups. Unfortunately, certain groups, such as African Americans, are inadequately represented in much of the available data and in current clinical trials. Recently, investigators have begun employing new messaging approaches to increase diversity in clinical trial enrollment. These messages are typically designed to inform, with no appeal for specific groups to act. Very little is known about the potential impact of inclusion appeals--direct appeals to historically marginalized groups calling on their need to be included in research studies. Applying the science of appeals to recruitment messages may improve the effectiveness of educational videos and lead to greater participation in research. This pilot study proposes to empirically study whether an inclusion appeal increases attempts to enroll children in studies.

### 1.2 Name and Description of Investigational Product or Intervention

The intervention will be a short video segment added to an informational video about Pediatric Clinical Research Study that will be tailored to appeal to the need for an inclusive population of study participants in clinical trials. For this pilot study, we will target African/African American participants.

### 1.3 Findings from Non-Clinical and Clinical Studies

n/a

these videos and did not publish any evaluation of the message's effectiveness at conveying its intended message. For example, a recent study by Skinner and colleagues investigated the role of an educational video on clinical trial enrollment among ethnic minorities. It showed no effect; however, it utilized a DVD-based intervention that was only watched by half the participants, which the authors acknowledged as a limitation. Finally, none of these projects appear to have included any sort of message that specifically appealed to a target audience. *Appeals* are a well-established approach in communication that utilize evidence or emotional triggers to persuade the receiver to change his or her behavior.

## 1.5 Compliance Statement

This study will be conducted in full accordance all applicable Children's Hospital of Philadelphia Research Policies and Procedures and all applicable Federal and state laws and regulations including 45 CFR 46, 21 CFR Parts 50, 54, 56, 312, 314 and 812 and the Good Clinical Practice: Consolidated Guideline approved by the International Conference on Harmonisation (ICH). All episodes of noncompliance will be documented.

The investigators will perform the study in accordance with this protocol, will obtain consent and assent, and will report unanticipated problems involving risks to subjects or others in accordance with The Children's Hospital of Philadelphia IRB Policies and Procedures and all federal requirements. Collection, recording, and reporting of data will be accurate and will ensure the privacy, health, and welfare of research subjects during and after the study.

## 2 STUDY OBJECTIVES

Our research objective is to identify components of video messages that motivate behavior change.

### 2.1 Primary Objective (or Aim)

The primary objective is to compare intent to enroll in a research discovery site after seeing a video with an inclusion appeal versus one without such an appeal—focusing on parents and guardians who identify as African or African American.

---

 Jeannine S. Skinner et al., “The Impact of an Educational Video on Clinical Trial Enrollment and Knowledge in Ethnic Minorities: A Randomized Control Trial,” *Frontiers in Public Health* 7 (2019): 104, <https://doi.org/10.3389/fpubh.2019.00104>.

 Joseph Petraglia, “The Importance of Being Authentic: Persuasion, Narration, and Dialogue in Health Communication and Education,” *Health Communication* 24, no. 2 (March 2009): 176–85, <https://doi.org/10.1080/10410230802676771>.

 Melanie B. Tannenbaum et al., “Appealing to Fear: A Meta-Analysis of Fear Appeal Effectiveness and Theories,” *Psychological Bulletin* 141, no. 6 (November 2015): 1178–1204, <https://doi.org/10.1037/a0039729>.

 Graton Aurélien and Mailliez Melody, “A Theory of Guilt Appeals: A Review Showing the Importance of Investigating Cognitive Processes as Mediators between Emotion and Behavior,” *Behavioral Sciences (Basel, Switzerland)* 9, no. 12 (November 20, 2019): E117, <https://doi.org/10.3390/bs9120117>.

## **2.2 Secondary Objectives (or Aim)**

The secondary objective of this study is to assess message effectiveness and targetedness of a video inviting African/African American parents to participate in clinical trials involving their children.

## **3 INVESTIGATIONAL PLAN**

### **3.1 General Schema of Study Design**

This project will include two phases, each of which is described below. The first phase of the study is designed to have members of the CHOP patient community review and evaluate the video and inclusion appeal message. Once the video has achieved a high level of perceived effectiveness, we will begin the second phase. The second phase of the study will be a 3-arm randomized controlled trial, focusing on parents of children cared for in CHOP primary care clinics who self-identify as African Americans proficient in verbal and written English, and with no history of prior trial participation.

#### **3.1.1 Trial**

The study will take place in primary care clinics throughout the CHOP ambulatory care system.

Because this pilot will assess the impact of a video, the first phase of the study will consist of work leading to videos used through the rest of the study. This phase will leverage work currently underway at the Children's Hospital of Philadelphia (CHOP) to construct a library of messages aimed at improving parents' knowledge about, and willingness to participate in, clinical research. Although some of these videos are constructed, none focus on the specific question that will be the focus of this research. We will work closely with a subset of CHOP's Research Family Partners (RFP), who will assist with all aspects of script development, tailoring to the diverse community served by CHOP, and evaluation plan. The RFP will help us to identify at least two patient families who identify as African American who have participated in trials to interview and record for this project. The rough video will be validated by a sample of RFP members who identify as being from a historically marginalized group. We will primarily evaluate perceived message effectiveness, using the six-item survey developed by KC Davis and colleagues. We will make iterative changes to the rough video until its perceived effectiveness averages 4.0 or greater on a 1–5 scale. We will create a separate video segment for the inclusion appeal. This separate segment will be reviewed and approved by the RFP using a similar method before being edited into a copy of the video. Once the video and inclusion appeal messages are finalized (we anticipate this taking no more than 3 meetings), we will finalize the two videos and complete post-production to incorporate background music, improve color, audio balance and edit transitions.

Once the videos are created and validated, we will conduct a 3-arm randomized trial, focusing on parents with children cared for by CHOP who self-identify as African or African Americans proficient in verbal and written English, and with no history of prior trial participation. We will work with the RFP to identify the ideal settings for recruitment, which may include clinics, community settings, and online social media sites. We are currently

planning to invite participants to complete the study at a Penn or CHOP facility, rather than at home. Study participants will complete materials using an online survey completion and video display system (REDCap or Qualtrics). Each participant will complete questions about their age, gender identity, race/ethnicity, education attainment, and their child's age and gender identity. We will then ask a subset of questions from the NIH Health Information National Trends Survey to assess clinical trials knowledge. After these questions, all eligible participants will be randomly show either one of two videos (with or without the inclusion appeal) followed by a short survey about perceived effectiveness of the message or taken directly to the final question. The final question will ask if they are willing to receive messages about potential clinical trials for their child. If they select yes, they will be taken to the enrollment screen for the registry above and will be given assistance by the research coordinator to help them complete the process if required.

Each participant will be paid \$20 for participating in the study. The primary outcome will be intention to join a research registry called the Research Discovery Finder that notifies parents about research studies. We will measure attempts to join, rather than joining, in case the process of joining is too complicated or confusing. Based on data from two similar studies in adults we will need approximately 30 completed surveys per group to have 80% power to detect a difference with a 0.05 significance level. Results will be reported using standard descriptive statistics. Between group differences in intent to enroll will be analyzed using chi-square analysis, with significance set at the 0.05 level. We will use a series of one-way between-group analyses of variance to determine the impact of the experimental video on dependent variables.

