## **4.1 Visit 1 (Phase 2)**

Detailed description of study visit including all procedures.

Potential participants will be invited to enroll in the study based on scheduled information and self-identified race/ethnicity.

Upon arrival to clinic, potential participants will complete a brief screening form related to the inclusion criteria (English proficiency, able to watch a video or see an image, African/African American race). If inclusion criteria are met, they will receive informed consent form (with review and discussion) and be asked to sign it.

Participants will complete an online survey containing: (1) demographic questions (their age, gender identity, education attainment, and their child's age and gender identity); (2) clinical trials knowledge, using a subset of questions from the NIH Health Information National Trends survey

Participants will be randomly shown either: (1) one of two videos (with or without the inclusion appeal) followed by a short survey about perceived effectiveness of the message; or (2) a paragraph and image describing the CHOP Research Discovery Finder.

Participants will be asked if they are willing to receive messages about potential clinical trials for their child from the CHOP Research Discovery Finder. If they select yes, they will be taken to the enrollment screen for the registry above and will be given assistance by the research coordinator to help them complete the process if required.

Each participant will be paid \$20 for participating in the study.

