## **5.3 Statistical Methods**

### **5.3.1 Baseline Data**

Baseline and demographic characteristics will be summarized by standard descriptive summaries (e.g. means and standard deviations for continuous variables such as age and percentages for categorical variables such as gender).

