### **5.3.2 Efficacy Analysis**

For our assessment of differences between the three groups' intent to enroll, we will use a series of one-way between-group analyses of variance to determine the impact of the experimental video vs. control video vs. no video on enrollment intent.

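### Clinical-trials knowledge is measured before exposure in every arm, but neither stated analysis of intent adjusts for it; precision may be lost if knowledge predicts intent

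*Combined protocol and SAP*

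**What the plan says.** Section 3.1.1 places the knowledge items, "a subset of questions from the NIH Health Information National Trends Survey to assess clinical trials knowledge", ahead of the randomised material: "After these questions, all eligible participants will be randomly show either one of two videos", or else participants go straight to the final question. Section 4.1 (Phase 2) keeps the same order and lists "clinical trials knowledge, using a subset of questions from the NIH Health Information National Trends survey" in the survey that comes before the video or description.

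The outcome is in effect yes/no: "The primary outcome will be intention to join a research registry called the Research Discovery Finder", measured as an attempt to join. Two analyses are given for it. Section 3.1.1 says "Between group differences in intent to enroll will be analyzed using chi-square analysis". Section 5.3.2 says "we will use a series of one-way between-group analyses of variance". Neither has a covariate.

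The only stated use of baseline data is in 5.3.1: "Baseline and demographic characteristics will be summarized by standard descriptive summaries". No objective, endpoint or analysis in sections 2 or 5 mentions the knowledge items, and their number and scoring are not given.

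**The concern.** A baseline measure that predicts the outcome can be put in the model to reduce the residual variance of the randomised comparison, with no extra data or participants. Knowledge of trials is a plausible predictor of willingness to join a trials registry. Section 3.1.1 itself links the two when it describes CHOP's message library as intended to raise both knowledge and willingness. That supports plausibility but says nothing about strength.

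The trial is small, at 30 or 20 per group depending on the section, so modest gains would be welcome. The covariate also has to be named before outcome data are seen, because adding it later invites selective reporting. At stake is the width of the interval on the appeal effect and a few points of power. The validity of the comparison is not in question.

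**Working it through.** **1. The plan's own figure.** Section 3.1.1 gives 30 completed surveys per group for 80% power at the 0.05 level; section 5.4 gives 20 for the same power and level. Neither states arm rates or an effect size, so neither can be reproduced. Solving backwards (two-sided 0.05, equal arms, two-arm comparison, no continuity correction):

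n = [1.96·√(2·p̄·(1−p̄)) + 0.842·√(p1(1−p1) + p2(1−p2))]² / (p2−p1)²

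With p1 = 0.30 and p2 = 0.654, p̄ = 0.477. The numerator is (1.96 × 0.706 + 0.842 × 0.661)² ≈ 3.77, the denominator is 0.354² ≈ 0.125, and n ≈ 30. For first-arm rates of 0.10 to 0.50, 30 per group detects differences of about 31 to 35 points, and 20 per group about 39 to 43 points.

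**2. Analytic size of the gain.** If knowledge explains a share R² of the outcome variance, the variance of the arm difference is multiplied by about (1−R²)(1 + 1/85) at N = 90, or (1−R²)(1 + 1/55) at N = 60. The second factor is the cost of estimating one more coefficient.
- R² = 0: 1.012 (N = 90) and 1.018 (N = 60), a small loss.
- R² = 0.05: 0.961 at N = 90.
- R² = 0.10: 0.911.
- R² = 0.20: 0.809.
- Break-even R²: about 0.012 at N = 90 and 0.018 at N = 60.

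Starting from exactly 80% power at 30 per group, and ignoring the small estimation cost, power becomes 82.1%, 84.1% and 88.3% at R² = 0.05, 0.10 and 0.20. No R² is given in the documents; these values are assumptions.

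**3. Simulation on the yes/no outcome.** Assumptions: logistic model with intercept −0.2; knowledge slope 0, 0.5 or 1.0 per SD; appeal log-odds ratio 1.5; three equal arms; 4,000 trials per scenario. At slope 0 the intent rates are 1/(1+e^0.2) = 0.45 and 1/(1+e^−1.3) = 0.79, a gap of about 34 points, which is close to what 30 per group can detect in step 1. The adjusted analysis is a linear model with arm and knowledge and HC3 standard errors. The comparator is the planned test, an uncorrected two-arm chi-square.

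| Per arm | Slope per SD | Chi-square power | Adjusted power | Change (points) |
|---|---|---|---|---|
| 30 | 0 | 78% | 77% | about −1 |
| 30 | 0.5 | 74% | 75% | about +1 |
| 30 | 1.0 | 64% | 70% | about +6 |
| 20 | 0 | 61% | 58% | about −3 |
| 20 | 0.5 | 57% | 56% | about −1 |
| 20 | 1.0 | 47% | 52% | about +5 |

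At 30 per arm the variance of the appeal-minus-plain risk difference falls by about 3% (slope 0.5) to 15% (slope 1.0). At slope 0 it rises by 1% to 2%. By step 2 these reductions correspond to R² of about 1 − 0.97/1.012 = 0.04 and 1 − 0.85/1.012 = 0.16. Type I error of the adjusted test stays at about 4% to 5%. The simulation error on one power figure near 75% is √(0.75 × 0.25/4000) ≈ 0.7 points, so changes of 1 point are barely distinguishable from none.

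**4. Choice of comparator.** At 30 per arm the chi-square and the unadjusted HC3 test have the same power. At 20 per arm the unadjusted HC3 test is weaker than chi-square (53% against 57% at slope 0.5; 44% against 47% at slope 1.0). Comparing adjusted with unadjusted HC3 at 20 per arm would therefore overstate the gain over the planned test.

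**5. Coarse scores.** Step 3 treats knowledge as continuous and free of error. With slope 1.0 and 30 per arm, a three-level score cuts the variance by about 12% and a two-level score by about 8%. With slope 0.5 and two levels, the cut is about 1% to 2%, with little or no gain in power.

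**The case against.** The strongest reply is that nothing is wrong with the plan as written. Randomisation makes the unadjusted comparison unbiased, chance imbalance is already allowed for in its type I error, and an unadjusted test is a legitimate choice for a self-described pilot. All of this stands.

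A reader might infer that the trial certainly loses precision, or that imbalance in knowledge at this size would distort the result. The documents support neither. No correlation between knowledge and intent is reported, and imbalance between arms adds noise, not bias. It is frequent (the two video arms would differ by more than 0.25 SD in about 33% of trials at 30 per arm and 43% at 20), but that only shows where adjustment could help if the score is prognostic.

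Three further limits also stand:
- A subset of survey items may make a coarse score, so the 15% figure is near a best case for the slopes assumed.
- The score is planned for everyone but not guaranteed: the early termination section provides for withdrawal after a single answered question.
- The schedule of procedures and 7.6.2 place randomisation at screening or consent, whereas the abstract, 3.1.1 and 4.1 place it after the questions. Knowledge precedes exposure in either order, but the sections should be reconciled.

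The reply does not remove the basic observation: the measure is collected, no analysis uses it, and no reason for collecting it is given.

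**Conclusion.** The point holds as a conditional matter of efficiency. The trial may give up precision if knowledge predicts intent; whether it does cannot be established from the documents.

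At 30 per arm, the figure that matches the 90 evaluable subjects in 3.1.4, the balance favours adjustment: roughly 1 to 6 power points gained under the assumed slopes, against about 1 point lost if the score is uninformative. At 20 per arm the case is weaker, because the change against chi-square runs from −3 to +5 points over slopes of 0 to 1.0. These figures rest on the assumed slopes, the assumed appeal effect, equal allocation and a continuous score.

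The point ranks below three problems in the same sections: chi-square against ANOVA, 30 against 20 per group, and the missing effect size. Section 5.3.2 must be rewritten to settle the first of these, and that is the natural time to decide on a covariate.

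**What to change.** In 5.3.2:
- Define one knowledge score: the number of correct answers on a named list of items, with a simple rule for missing items, such as imputing the mean taken across arms.
- Analyse intent with a linear model containing all three arms and this score as the only covariate, with HC3 standard errors. The one-way ANOVA already named there is the same model without the score.
- Report the appeal-minus-plain risk difference, which is the contrast in 2.1, with its 95% interval, alongside the three-group comparison in 5.1.
- Keep the unadjusted chi-square as a sensitivity analysis.

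The cost is a paragraph of text, an agreed scoring and missing-item rule before data are seen, and a few lines of R, which 7.2 already names. The statistical risk is the loss given above for a score that turns out not to be prognostic.

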# **5 STATISTICAL CONSIDERATIONS**

## **5.1 Primary Endpoint**

The primary endpoint will be the difference in intent to enroll between the three groups.

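### Only the video arms rate the message before the registry question, so the video versus no-video part of the primary endpoint cannot be attributed to the video alone

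*Combined protocol and SAP*

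**What the plan says.** Three places give the order of events in Phase 2, and they agree about the video arms.

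- **Abstract, Study Interventions and Measures.** The no-appeal arm is "video without inclusion appeal, questions about the perceived effectiveness of the video", and the appeal arm is described in parallel. The third arm is only "Short description of the registry", with no rating questions.
- **Section 3.1.1.** Participants see a video "followed by a short survey about perceived effectiveness of the message or taken directly to the final question". That final question is the registry question.
- **Section 4.1, Visit 1 (Phase 2).** Participants get "one of two videos (with or without the inclusion appeal) followed by a short survey about perceived effectiveness of the message", or else "a paragraph and image describing the CHOP Research Discovery Finder". The registry question comes next.

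The use made of the three arms is set elsewhere. Section 5.1 states: "The primary endpoint will be the difference in intent to enroll between the three groups". Section 5.3.2 plans the analysis "to determine the impact of the experimental video vs. control video vs. no video on enrollment intent". Section 2.1 is narrower, and sets out to "compare intent to enroll in a research discovery site after seeing a video with an inclusion appeal versus one without such an appeal". Section 5.2 identifies the rating instrument as a six-question survey, compared between the two video arms only.

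Nowhere does the third arm receive comparable items, are the items placed after the registry question, or is the difference acknowledged.

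**The concern.** Rating a message asks the viewer to reflect on it and to commit to a judgement, immediately before being asked to act on it. That could raise willingness to sign up or lower it. In this plan the rating task always accompanies a video and never accompanies the description. Any effect of the rating task on sign-up would therefore be read as an effect of the video, or would hide one, and no analysis of the planned data can tell these apart.

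The third arm is also described in two ways. Section 3.1.1 sends it straight to the registry question, while the Abstract and section 4.1 (Phase 2) show it a description first. What the comparator consists of is therefore not settled either.

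**Working it through.** **1. What each contrast compares**

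| Contrast | One side | Other side | Differs by |
|---|---|---|---|
| Appeal vs no appeal (2.1) | Video with appeal + items | Video without appeal + items | Appeal segment only |
| Video vs no video (part of 5.1 and 5.3.2) | Video + items | Description, or nothing, without items | Video and items together |

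The first row is clean with respect to the items. The second is not.

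**2. Inputs for an illustration**

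The documents give no yes rates, no item wording and no evidence on an item effect, so there is no figure of the plan's to reproduce here. From the plan: 30 completed surveys per group (3.1.1) or 20 (5.4), and a 0.05 level. Assumed: no-video yes rates of 30–70% in steps of 1 point, and an item shift of 0, 5, 10 or 15 points, up or down, applied equally to both video arms.

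**3. Method**

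Exact enumeration of three independent binomial counts. With yes proportions p1, p2, p3, their mean p̄ and n per arm, the Pearson statistic on 2 df is

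X² = n · [(p1 − p̄)² + (p2 − p̄)² + (p3 − p̄)²] / [p̄(1 − p̄)].

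The test rejects when X² exceeds 5.99. A one-way ANOVA on the 0/1 outcome gives the same rates.

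**4. No true video effect: probability that the three-group test is significant**

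| Item shift | 30 per arm | 20 per arm |
|---|---|---|
| 0 | 4.8–5.2% | 5.0–5.2% |
| 5 points | 6.3–7.0% | 5.9–6.6% |
| 10 points | 11.1–14.1% | 9.1–11.3% |
| 15 points | 20.0–29.7% | 14.8–21.2% |

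These are false positives only if the result is read as the effect of the video. As a comparison of packages, they are correct detections.

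**5. Masking**

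Suppose the video truly raises intent from 50% to 70% in both video arms, and the items take 10 points away, leaving 60%.

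- 30 per arm: power falls from 36.7% to 11.4%.
- 20 per arm: power falls from 25.4% to 9.2%.

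**6. Appeal versus no appeal**

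With equal true rates anywhere from 15% to 85%, the two-arm chi-square test rejects in 4.8–5.3% of trials at 30 versus 30 and 4.3–5.3% at 20 versus 20. A shift common to both video arms therefore creates no false appeal effect.

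The size of a real appeal effect could still differ after rating. Take 50% versus 70% without items, and let the items act with one odds ratio in both arms.

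- No-appeal rate moved up to 60%: odds ratio (0.6/0.4)/(0.5/0.5) = 1.5. Appeal odds 1.5 × 0.7/0.3 = 3.5, a rate of 77.8%. Difference 17.8 points.
- No-appeal rate moved down to 40%: odds ratio 0.667. Appeal odds 0.667 × 2.333 = 1.556, a rate of 60.9%. Difference 20.9 points.

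Both are close to the original 20 points.

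**The case against.** The strongest reply is that no stated objective depends on the affected contrast. Section 2.1 asks about appeal versus no appeal, and section 1.2 defines the intervention as the added segment. Both video arms get the same items, so that question is answered cleanly. The Abstract also lists the rating questions openly as part of the two video interventions, so the three-arm comparison is a legitimate comparison of packages with one imprecise label. Nothing in the documents shows that six rating items change willingness to join, and a 5-point shift would barely matter. In the masking example, power is only 37% before any item effect, so most of the missed detection there comes from the small sample. Finally, moving the items could disturb the ratings, which are the secondary endpoint.

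Most of this stands, and it limits the point. It does not remove it. Section 5.1 makes the three-group difference the primary endpoint, and 5.3.2 attributes it to the videos rather than to videos plus questions. Section 2 also says the aim is to identify which components of video messages change behaviour, and that cannot be done for two components that always occur together. The unknown size of the item effect is a reason to balance or label the arms, because the trial itself cannot estimate it.

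**Conclusion.** The concern holds, within limits. The video versus no-video part of the primary endpoint, and any three-group result driven by it, cannot be attributed to the video alone. The primary objective is not confounded, although the appeal effect is estimated among people who have just rated the message.

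The size is unknown. Under the assumed shifts the consequence ranges from negligible at 5 points to a three-group rejection rate of 20–30% at 15 points with 30 per arm. Those figures assume no video effect, an equal shift in both video arms and no-video yes rates of 30–70%. They show what such a shift would do and are not evidence that it exists. This is a worthwhile improvement to a pilot, and it does not invalidate the design.

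**What to change.** First reconcile section 3.1.1 with the Abstract and section 4.1 (Phase 2) on what the third arm sees. Then choose one of the following.

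1. **Matched items.** In the Qualtrics flow, give the description arm parallel items about the description, before the registry question. This needs something to rate, so it presupposes that the third arm sees a description. Cost: up to six adapted questions in one arm, and a little more time where the plan already expects people to run out of it (Early Termination Study Visit; 5.4). Rating a description may not act exactly like rating a video, and the appeal effect is still estimated after rating.

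2. **Reorder.** Record the yes/no registry answer immediately after the video or description in all arms, and define that answer in 5.1 as the primary outcome. Put the effectiveness items directly after it and before the enrollment screen. Use this only if the recorded answer is the outcome. If attempts to join are counted at the enrollment screen, the items would still precede the outcome in the video arms only, and option 1 is needed. Cost: one survey block moved and one sentence in 5.1. There are two side effects:
   - Ratings may be coloured by the answer just given, which should be stated for the secondary endpoint. As an assumed example, a 20-point sign-up difference and a rating 0.5 higher after yes move the arm difference by 0.20 × 0.5 = 0.10 on a 1–5 scale. The range is 0.10 × 0.25 = 0.025 to 0.30 × 1.0 = 0.30.
   - Items placed after the enrollment screen would be lost according to the outcome. If 20% of yes responders skipped them and sign-up were 50% versus 70%, losses would be 0.20 × 0.50 = 10% versus 0.20 × 0.70 = 14%, or 3.0 versus 4.2 of 30. Placing them before that screen avoids this.

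3. **Relabel.** If neither change is made, state in 5.1 and 5.3.2 that the contrast is video plus rating items versus description, and report it that way. Cost: one sentence.
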